7.2.4 Adverse Events of Special Interest (AESI)

Treatment-emergent AESIs determined to be of autoimmune etiology based on decision of the DSMB will be summarized by SOC and PT, listed by individual participant.

The incidence rate of treatment emergent AESIs will be summarized and analysed in the similar manner as described in [Section 7.2.3](#).

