5.2. Exclusion Criteria

Individuals meeting any of the following criteria will be excluded from study participation:

1. Use of any investigational or nonregistered product (drug, vaccine, device, or combination product) within 30 days preceding the dose of study vaccine, or planned use during the study through Month 13.
2. Positive test result on urine drug screen, any evidence of ongoing drug abuse or dependence (including alcohol), or recent history (over the past five years) of treatment for alcohol or drug abuse.
3. Chronic administration (defined as >14 days) of immunosuppressants or other immune-modifying drugs (includes oral or parenteral corticosteroids, eg, a glucocorticoid dose exceeding 10 mg/day prednisone or equivalent) within six months prior to the vaccine dose; inhalation use (eg, for seasonal allergies) is permitted.
4. Planned administration of any commercially-available vaccine from seven days prior to the first study vaccination through two weeks after the last vaccination.

5. Previous anaphylactic reaction, severe systemic response, or serious hypersensitivity to a prior immunization or a known allergy to synthetic ODNs, aluminum, formaldehyde, benzethonium chloride (phemerol), or latex.
6. History of anthrax disease, suspected exposure to anthrax, or previous vaccination with any anthrax vaccine.
7. Have a tattoo/scar/birthmark or any other skin condition affecting the deltoid area that may interfere with injection site assessments.
8. A positive blood test for hepatitis B surface antigen, hepatitis C antibody, or human immunodeficiency virus (HIV) HIV-1 or HIV-2 antibodies.
9. Any confirmed or suspected immunodeficiency condition (congenital or secondary) or autoimmune disease based on medical history and PE, eg, Guillain-Barré.
10. A family history of congenital or hereditary immunodeficiency.
11. Major congenital defects or serious chronic illness, including any cancer other than the following: a) any non-metastatic cancer (excluding hematologic malignancies) or melanoma of which the participant has been disease-free for at least five years and b) localized skin cancer, resected (including squamous cell and basal cell carcinomas).
12. Acute disease at the time of enrollment.

Note that screening lab tests may be delayed to allow the resolution of a transient acute condition or the subject may be rescreened according to procedures under [Section 5.4](#).

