8.4. Data Monitoring Committee(s)

8.4.1. Data Safety Monitoring Board

Independent safety oversight will be provided by a DSMB, which will be notified of significant AEs (eg, SAEs, severe AEs recorded on eCRF, potential AESIs of autoimmune etiology, or any other events the MM deems medically relevant) as determined by the MM on an ongoing basis, including any that result in study halt based on prespecified stopping rules (refer to [Section 7.1](#)). The DSMB will comprise at least three voting members, to include one expert in immunology to specifically support the evaluation of potential AESIs for autoimmune etiology.

All DSMB reviews will be performed with blinded data, unless otherwise requested by the DSMB Chair. The DSMB will make recommendations regarding the safety of continuing enrollment and dosing. Study enrollment and dosing may be interrupted at the request of the DSMB Chair if it is believed that an AE represents a significant safety concern requiring interruption of dosing pending full DSMB evaluation.

A planned interim DSMB safety data review will be conducted after the first 500 participants have completed the Day 29 visit, comprising all safety evaluations through two weeks after the second vaccination. The DSMB will be supported by a (non-voting) unblinded statistician who will provide safety data (also demographics/baseline characteristics and protocol deviations) and otherwise assist in review activities as required.

The DSMB Chair will receive and evaluate each SAE, each severe AE (reported on the AE eCRF), and potential AESIs of autoimmune etiology. In addition, the MM may notify the DSMB Chair of any other medically relevant events (based on regular medical monitoring activities) for their review. The DSMB Chair will determine if an *ad hoc* review, in addition to the planned interim review, by the entire DSMB is necessary. An *ad hoc* review by the entire DSMB, when it occurs, may be focused on a single participant or on data for all participants. The operations of

the DSMB will be detailed in a DSMB Charter, to be finalized prior to screening of the first participant.

At least one DSMB member will be an expert in autoimmune disorders (eg, rheumatologist, immunologist). This member will review, on a blinded basis, all potential AESIs to assess cases for autoimmune etiology, if pre-existing or new onset, and relationship to the IP. Details on the recording of the AESI assessment outcomes will be detailed in the DSMB Charter.

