9.1.3. Adverse Event of Special Interest

For this trial, an AESI is defined as any AE having an autoimmune etiology. Refer to [Appendix B](#) for a list of AESI terms defined by FDA's CBER that are potentially associated with autoimmune disease, and might represent a safety signal for vaccine-associated autoimmunity. Potential AESIs will be assessed by a member of the DSMB having expertise in this area (refer to [Section 8.4.1](#)). Once assessed as autoimmune in nature, the event will be considered as a confirmed AESI and recorded on the AE eCRF.

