2.2.3.6 Data Safety Monitoring Board

Independent safety oversight will be provided by a DSMB, which will be notified of significant AEs (eg, SAEs, severe AEs recorded on eCRF, potential AESIs of autoimmune etiology, or any other events the MM deems medically relevant) as determined by the Medical Monitor on an ongoing basis. The DSMB will comprise at least three voting members, to include one expert in immunology to specifically support the evaluation of potential AESIs for autoimmune etiology, if pre-existing or new onset, and relationship to the study product. All DSMB reviews will be performed with blinded data, unless otherwise requested by the DSMB Chair. The operations of the DSMB will be detailed in a DSMB Charter.

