4.4 Handling of Missing Data

Unless otherwise specified, no imputation will be made for missing data.

Immunogenicity response TNA NF₅₀ values which are below the lower limit of quantification (LLOQ) will be handled according to the specifications in Section 6.

Participants in the PP Population who have missing immunogenicity data at Day 29 will be excluded from Day 29 immunogenicity analysis, with the assumption that the missingness is

completely at random since the participants will not have any knowledge about their immune response in terms of TNA NF₅₀.

Descriptive safety presentations will be based on observed cases. To permit proper tabulation of AEs or medications, if appropriate, the following conventions will be used for imputation of completely and partially missing dates:

- For start date missing completely, impute the date of first vaccination
- For start date with missing day only, impute the 1st of the month unless month is same as month of first vaccination then impute the date of first vaccination.
- For start date with missing month and day, impute 1st January unless year is the same as the date of first vaccination then impute the date of first vaccination
- For end date missing completely, impute date of last contact
- For end date with missing day only, impute the last day of the month. If the month of the end date is same as month of last contact then impute the date of last contact
- For end date with missing month and day, impute 31st December or date of last contact, whichever is earlier
- If the end date is not missing and the start date is after the end date after missing value calculation, the end date will be used for the start date.
- An AE with completely missing both start and end dates, or with the start date missing and end date later than the date of first vaccination, will be considered to be treatment- emergent.

Missing start/end dates will appear as missing in the participant data listings.

Unless otherwise specified, no other imputation will be made for missing data.

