7.2.1 Overall Summary of TEAEs

A treatment-emergent adverse event (TEAE) is defined as an AE that presents after the initiation of treatment or any AEs already present that worsen in either intensity or frequency following treatment. For programming purpose, any AEs with start date on or after the start date of the first vaccination will be counted as treatment-emergent. AEs with missing start dates, but with end dates later than the date of first vaccination will also be counted as treatment emergent.

An overall summary table with the following TEAE categories will be provided:

- TEAEs
- Vaccine-related TEAEs
- Grade 3 or 4 TEAEs
- Vaccine-related Grade 3 or higher TEAEs
- Serious TEAEs
- Serious vaccine-related TEAEs
- Death
- TEAEs leading to discontinuation of vaccination
- TEAEs leading to study withdrawal
- AESIs
- Vaccine-related AESIs

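### The DSMB expert's pre-existing or new-onset classification of each AESI is not used in the AESI incidence or relative risk

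*SAP*

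**What the plan says.** **The classification.** Protocol 8.4.1 has a DSMB member with autoimmune expertise review all potential AESIs blinded, "to assess cases for autoimmune etiology, if pre-existing or new onset, and relationship to the IP". SAP 2.2.3.6 repeats the task: "evaluation of potential AESIs for autoimmune etiology, if pre-existing or new onset, and relationship to the study product".

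**What confirms an AESI.** Only the first of those judgements does. Protocol 9.1.3: "Once assessed as autoimmune in nature, the event will be considered as a confirmed AESI and recorded on the AE eCRF".

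**What is analysed.** SAP 7.2.4: "Treatment-emergent AESIs determined to be of autoimmune etiology based on decision of the DSMB will be summarized by SOC and PT". The section then applies the method of SAP 7.2.3: within-group proportions with exact Clopper-Pearson limits, and a relative risk of AV7909 to BioThrax with an exact unconditional 95% CI, without formal testing. Protocol 10.6.2 plans the same tabulation and relative risk.

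**How treatment emergence is programmed.** SAP 7.2.1: "any AEs with start date on or after the start date of the first vaccination will be counted as treatment-emergent". SAP 4.4 adds: "For start date missing completely, impute the date of first vaccination". Under the same section, a start date lacking the day (in the month of dose 1), or lacking month and day (in the year of dose 1), also becomes the date of dose 1.

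**Entry and baseline testing.** Protocol 5.2 excludes "autoimmune disease based on medical history and PE, eg, Guillain-Barré". The screening tests in Protocol 8.1.1 do not include RF, ANA, anti-dsDNA or TSH. These are first drawn on Day 1 before dosing (Protocol 8.1.2 and 8.3.2).

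**The concern.** A blinded onset judgement is planned for every potential AESI, and the analysis it bears on most directly ignores it. Entry does not screen serologically for autoimmune disease, so undiagnosed disease can be enrolled. If it surfaces later, the expert may call it pre-existing, yet it still counts as treatment-emergent when its start date is recorded or imputed on or after dose 1. Neither document says how to date such disease.

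Protocol 2.3.2 names autoimmunity as a potential risk of CpG adjuvants and gives it as the reason for follow-up to Month 13. AESI incidence is a secondary endpoint. Mixing disease already present at entry with disease arising after vaccination overstates the incidence of new autoimmune disease in both arms. It can also make a real excess look smaller on the ratio scale.

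**Working it through.** **Step 1. Follow one case through the rules.** Take a participant with undiagnosed autoimmune disease at entry, found after Day 1 and still ongoing.

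- Exclusion: passes, because history and PE show nothing.
- DSMB review: autoimmune, pre-existing. It is a confirmed AESI, because new onset is not required.
- Start date recorded after dose 1: treatment-emergent, so counted.
- Start date wholly missing, or partial within the month or year of dose 1: imputed to dose 1, so counted.
- Start date recorded before dose 1, with no worsening: not counted.

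The expert's onset decision plays no part in any branch. Only the recorded date does.

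**Step 2. The plan's own safety figure.** Protocol 10.1 and SAP 2.4 state a 95% probability of detecting an AE with rate 0.1% in 3000 participants.

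- 1 − (1 − 0.001)^3000 = 95.03%.
- With 3300 × 0.9 = 2970: 94.88%.

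The figure reproduces, and this point does not affect it. No figure specific to AESIs is given.

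**Step 3. Effect on the relative risk.** Let r_AV and r_BT be the new-onset rates and b the proportion with counted pre-existing disease, taken as equal in both arms. Then

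counted RR = (r_AV + b) / (r_BT + b).

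The documents give none of these rates for AV7909 or BioThrax. All values below are assumptions.

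| b, each arm | 0.3% vs 0.1% (true RR 3) | 0.5% vs 0.1% (true RR 5) |
|---|---|---|
| 0.1% | 0.4/0.2 = 2.00 | 0.6/0.2 = 3.00 |
| 0.2% | 0.5/0.3 = 1.67 | 0.7/0.3 = 2.33 |
| 0.3% | 0.6/0.4 = 1.50 | 0.8/0.4 = 2.00 |
| 0.5% | 0.8/0.6 = 1.33 | 1.0/0.6 = 1.67 |
| 1.0% | 1.3/1.1 = 1.18 | 1.5/1.1 = 1.36 |

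If the true ratio is 1, it stays 1 and only the incidence is inflated.

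**Step 4. Counts and risk difference.** After 10% dropout the arms are about 3000 (from 3300) and 500 (550 × 0.9 = 495).

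- Pre-existing cases counted at b = 0.1%: 3.0 and 0.5.
- At b = 1.0%: 30 and 5.
- Risk difference: (r_AV + b) − (r_BT + b) = r_AV − r_BT. It stays at 0.2 or 0.4 percentage points.

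**Step 5. Does it change what the interval can show?** The chance that the interval lies above 1 was found by exact binomial enumeration at 3000:500, with a pooled score test and Fisher's test standing in for the exact unconditional interval.

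- True RR 3: 0.0% on the score test without pre-existing cases, at most 3.4% with them.
- True RR 5: 2.0% without, at most 8.8% with.
- At 3300:550 the largest value in any scenario is 10.7%.

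The chance is small in every scenario. With a 0.1% rate, the probability of no new-onset case among 500 BioThrax participants is 0.999^500 = 61%, in which case the ratio is infinite or undefined.

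**The case against.** **The Day 1 route is not documented.** A reader might infer that the trial's own Day 1 blood tests unmask disease that is then given a post-dose onset date. The documents do not say so. Results would normally arrive after vaccination, since samples go to a central laboratory and dosing must follow on the day of randomisation, but that is inference. Other rules point the opposite way. Under Protocol 9.2, events before dose 1 unrelated to study procedures go to medical history. Under SAP 3.4, the predose sample is itself the baseline. Under Protocol 8.3.2, a laboratory abnormality below Grade 3 becomes an AE only if it is a clinically significant change from baseline. This objection stands: the route is possible, not established.

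**The TEAE definition already excludes unworsened disease.** The sentence before the programming rule in SAP 7.2.1 covers events arising after treatment starts or worsening after it. True in concept, but the program uses dates, so misdated or undated onset gets through.

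**The SAP follows the protocol's endpoint.** The protocol defines an AESI by autoimmune etiology and counts from first vaccination. Protocol 2.3.2 also describes the risk as disease triggered in susceptible people, so latent disease that flares could be called pre-existing and still be signal. This stands. It argues against replacing the planned count, and it means b may not be equal in both arms: randomisation balances disease at entry, not flare or detection after dosing.

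**Few cases, descriptive analysis.** Participant listings (SAP 7.2.4) and the row for vaccine-related AESIs (SAP 7.2.1) help. Neither yields a new-onset rate, and relatedness is a different judgement from onset. Recording of the expert's outcomes is left to the DSMB Charter, which is not among the documents, but SAP 7.2.4's selection rule stands whatever the Charter says.

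**Conclusion.** The gap is real. An onset classification described in both documents is used in no analysis, so AESIs judged pre-existing enter the incidence and relative risk whenever their recorded or imputed start date is on or after dose 1.

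Incidence is inflated in both arms by however many such cases occur. The relative risk moves towards 1 only if a true excess exists and pre-existing cases are equally frequent in both arms. The size is unknown. The fall from 3 to between 2.0 and 1.5 illustrates assumed rates and does not predict this trial's result.

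Two further readings are tempting and unsupported. One is that the trial loses power to detect an autoimmune signal: the risk difference is unchanged, and the interval would rarely exclude 1 either way. The other is that new-onset events should replace the planned count because the CpG 1018 hepatitis B vaccine trial in Protocol 2.3.2 reported new-onset events. That trial is cited as background on risk, not as the standard for this endpoint.

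**What to change.** - Carry the DSMB expert's onset classification (new onset or pre-existing) into the analysis dataset.
- In SAP 7.2.4, keep the protocol-defined count of all confirmed treatment-emergent AESIs. Add the same incidence, exact CI and relative risk for new-onset AESIs.
- Show pre-existing cases separately, including any that worsened after vaccination, so that a flare of latent disease stays visible.
- State that disease traced to the Day 1 predose sample is dated as present at baseline unless it worsens after vaccination.

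The cost is one analysis variable, one extra table and a few lines of SAP text. The assessment is already planned, so no new data are needed, and the protocol-defined endpoint does not change.

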There is a potential for CpG ODN adjuvants to trigger autoimmune disease in susceptible individuals {[Segal et al 2000](#)}, possibly as a result of non-specific activation of T or B lymphocytes. No subjects in the completed AV7909 clinical trials have reported AEs related to autoimmune disorders. Additionally, no AEs suggestive of autoimmune disease have been reported in the reviewed published data on the CPG 7909-adjuvanted infectious disease vaccine trials. A number of these trials reported subjects with moderate, transient elevations above the normal range in anti-double stranded deoxyribonucleic acid (anti-dsDNA) values or positive antinuclear antibody (ANA) or mild elevations in rheumatoid factor (RF) following vaccination, which typically returned to normal by the next dose or end of the study and were not associated with clinical symptoms {[Ellis et al, 2010](#); [Mullen et al, 2008](#); [Cooper et al, 2005](#); [Cooper et al, 2004](#)}. In a phase 3 trial of Heplisav-B vaccine containing a different CpG ODN, CpG 1018, in subjects followed for 13 months after the first dose of vaccine, the incidences of new onset immune-mediated AEs (as reviewed by independent adjudicators) were not clinically different between the Heplisav-B group (0.1%; 4/5587) and the non-adjuvanted Energix-B group (0%; n=2781), nor were these AEs in the Heplisav-B group considered related to vaccination {[Heplisav-B Prescribing Information, 2017](#)}.

In oncology trials of CPG 7909 that typically have used higher doses and treatment durations than expected with AV7909 vaccine exposure (refer to the Investigator's Brochure for more details), autoimmune disease has been reported in multiple subjects, although causal attribution to the study product is complicated by comorbidities and concomitant products/therapies. The autoimmune conditions observed have included polyarthralgia, arthritis, Sjögren's Syndrome, autoimmune thyroiditis, vitiligo, Guillain-Barré syndrome, and ulcerative colitis.

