10.6.2. Adverse Events

All AEs will be coded to SOC and PT according to MedDRA. Treatment-emergent adverse events (TEAEs) are defined as AEs that present after the initiation of treatment or any AEs already present that worsen in either intensity or frequency following treatment. The incidences of TEAEs will be presented in tabular form by summary categories of TEAEs (eg, any TEAEs, any drug-related TEAEs, any Grade 3 or 4 TEAEs) and using the MedDRA coded terms of SOC and PT overall, by $\geq 2\%$ incidence in either group, and by severity (toxicity grade), seriousness, relationship to IP, and outcome (death, discontinuation of IP, study withdrawal) for each study group. A separate tabulation by MedDRA SOC and PT will be provided of treatment-emergent AESIs determined to be of autoimmune etiology based on decision of the DSMB. Participants having the same TEAE more than once will be counted in tabulations once for each PT and once within each SOC at the maximum severity and relatedness. An additional tabulation will be provided of TEAE incidences by MedDRA PT in decreasing frequency of the AV7909 (three lots pooled) group relative to the incidences in the BioThrax group. The incidences of AEs from the time of the first vaccination on Day 1 through Day 64, as well as incidences of AEs reported from Day 1 and up to Month 13 will be provided for AV7909 (three lots pooled) and BioThrax groups.

The proportions of participants with treatment-emergent SAEs and AESIs and associated two-sided 95% CIs will be provided for AV7909 (three lots pooled) and BioThrax groups. The relative risks for treatment-emergent SAEs and AESIs between AV7909 and BioThrax groups and associated 95% CIs will also be provided. No formal hypotheses testing will be conducted.

Separate listings will be prepared for AEs, deaths, SAEs, TEAEs leading to discontinuation of IP or study withdrawal, and AESIs.

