2.2 Study Design and Conduct

2.2.1 Overall Study Design

This is a phase 3, multicenter, randomized, double-blind, parallel-group trial designed to evaluate the lot consistency (using three consecutive lots), immunogenicity, and safety of a two-dose schedule of AV7909 (Days 1 and 15) administered IM in healthy adults for an indication of postexposure prophylaxis (PEP) of anthrax.

Healthy adults between 18 and 65 years of age (inclusive) will sign and date an informed consent form (ICF) and then be screened for eligibility for participation in the study 2 to 28

[figure not shown]
days prior to randomization. Participants meeting the entry criteria will be randomized 2:2:2:1 to one of four study groups on Day 1, as shown in Table 2. Randomization will be stratified by site. A representative racial distribution will be sought among recruited participants. Participants who are randomized and do not receive vaccination on the same day will be withdrawn from the study. The study schematic is provided in Figure 1.

Table 2 Study Groups

Group No./Treatment	Sample Size (N)	Day 1	Day 15	Day 29
1/AV7909 Lot 1	1100	AV7909 Lot 1 (IM)	AV7909 Lot 1 (IM)	Placebo (SC)
2/AV7909 Lot 2	1100	AV7909 Lot 2 (IM)	AV7909 Lot 2 (IM)	Placebo (SC)
3/AV7909 Lot 3	1100	AV7909 Lot 3 (IM)	AV7909 Lot 3 (IM)	Placebo (SC)
4/BioThrax	550	BioThrax (SC)	BioThrax (SC)	BioThrax (SC)
Total	3850			

IM = intramuscular injection in the deltoid muscle; SC = subcutaneous injection over the deltoid region. AV7909 = 0.5 mL AVA + 0.25 mg CPG 7909. Placebo=saline for injection. BioThrax = 0.5 mL AVA.

Figure 1 Study Design Schematic

IM = intramuscular; SC = subcutaneous. AV7909 is administered IM on Days 1 and 15, with placebo administered SC on Day 29. BioThrax is administered SC on Days 1, 15, and 29.

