7.2.3 Serious TEAEs

Serious TEAEs will be summarized by SOC and PT. Serious TEAEs will be summarized by relationship to IP, SOC, and PT for AV7909 (three lots pooled) and BioThrax group as well.

A participant data listing of all serious AEs (both TEAEs and non-TEAEs) will be provided.

The safety outcome measure used for the primary safety analysis is the incidence rate of serious TEAEs. The within-group proportion of participants with serious TEAEs and associated two-sided 95% CI (exact Clopper-Pearson confidence limits) will be provided for AV7909 (three lots pooled) and BioThrax group. The relative risk (ratio of proportion of participants with serious TEAEs in AV7909 vs. BioThrax group) with exact unconditional 95% CI will be provided for treatment comparison between the two groups. No formal hypothesis testing will be conducted.

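### The only planned between-group comparison of AESIs is a relative risk, which has no finite estimate or upper limit if no BioThrax participant has a confirmed AESI; add a risk difference and a zero-event rule

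*SAP*

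**What the plan says.** SAP 7.2.4 covers treatment-emergent AESIs that the DSMB has judged to be autoimmune. It tabulates and lists them, then defines the analysis by reference: "The incidence rate of treatment emergent AESIs will be summarized and analysed in the similar manner as described in" Section 7.2.3.

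Section 7.2.3 contains two relevant elements, written for serious TEAEs:
- Within each group: "The within-group proportion of participants with serious TEAEs and associated two-sided 95% CI (exact Clopper-Pearson confidence limits) will be provided" for pooled AV7909 and for BioThrax.
- Between groups: "The relative risk (ratio of proportion of participants with serious TEAEs in AV7909 vs. BioThrax group) with exact unconditional 95% CI will be provided".

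It adds: "No formal hypothesis testing will be conducted".

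Protocol 10.6.2 also plans proportions with 95% CIs for each group, and then: "The relative risks for treatment-emergent SAEs and AESIs between AV7909 and BioThrax groups and associated 95% CIs will also be provided". The safety paragraph of the protocol synopsis likewise names only the relative risk as a comparison. Neither document plans a risk difference for AESIs or says what is reported when one group has no event.

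The study randomises 3300 participants to AV7909 and 550 to BioThrax (SAP 2.2.1 and 2.4). AESI incidence through the 12-month call is a secondary endpoint (SAP 2.3.2).

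**The concern.** The relative risk divides by the proportion in the smaller group. Allocation is 6:1 and confirmed autoimmune events are expected to be rare, so the denominator may well be zero. The ratio then has no finite point estimate and no upper limit, and at 0/0 it is undefined.

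Autoimmunity is the theoretical risk that Protocol 2.3.2 attaches to CpG adjuvants, and it is the stated reason for follow-up to Month 13. For such a risk, the useful between-group statement is how large an excess the data still allow. A ratio over a zero denominator cannot give that bound. With no rule written down, the choice between a continuity correction, another measure or an entry of not estimable would be made after the data are seen.

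**Working it through.** **The plan's own rare-event figure.** Protocol 10.1 and SAP 2.4 give a 95% probability of detecting an AE with a true rate of 0.1% in 3000 AV7909 participants. Taking detection as at least one event: 1 - (1 - 0.001)^3000 = 95.03%. The figure reproduces. No matching figure is given for BioThrax or for AESIs.

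**Rates in the documents.** Protocol 2.3.2 reports that new-onset immune-mediated events over 13 months "were not clinically different between the Heplisav-B group (0.1%; 4/5587) and the non-adjuvanted Energix-B group (0%; n=2781"). That CpG adjuvant is a different one. 4/5587 = 0.0716%, printed as 0.1%. Protocol 2.2.3 reports no AESIs in the earlier AV7909 studies, in which 241 people received the combination. No rate is given for the Appendix B list, so the last three rows below are assumptions.

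**Probability of no BioThrax event.** P(0) = (1 - r)^550 and P(1) = 550 r (1 - r)^549.

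| True rate r | P(0 of 550) | P(1 of 550) |
|---|---|---|
| 4/5587 | 67.4% | 26.6% |
| 0.1% | 57.7% | 31.8% |
| 0.2% (assumed) | 33.3% | 36.6% |
| 0.3% (assumed) | 19.2% | 31.7% |
| 0.5% (assumed) | 6.3% | 17.6% |

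No event is more likely than not below 1 - 0.5^(1/550) = 0.126%. It is the single most likely count up to 1/551 = 0.18%. With 10% dropout (495 followed), P(0) is 70.1% at 4/5587 and 60.9% at 0.1%.

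**Splitting the zero case, with the same rate in both groups.**
- No event in either group, (1 - r)^3850: 2.1% at 0.1%, and 6.3% at 4/5587.
- No BioThrax event but at least one on AV7909: 57.7% - 2.1% = 55.6% at 0.1%, and 67.4% - 6.3% = 61.1% at 4/5587.

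**What the planned within-group intervals give (Clopper-Pearson).** 0/550: 0 to 0.67%. 3/3300: 0.02% to 0.27%.

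**What a risk difference gives (AV7909 minus BioThrax, Newcombe 95% CI).** With p the AV7909 proportion, l and u its Wilson limits, and u0 the Wilson upper limit for 0/550, the interval runs from p - sqrt[(p - l)^2 + u0^2] to u. Here u0 = 3.8415/553.8415 = 0.694%. For 3/3300, p = 0.0909%, l = 0.0309% and u = 0.267%, so the lower limit is 0.0909% - sqrt(0.0600^2 + 0.6936^2)% = -0.605%.

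| AV7909 | BioThrax | Difference | 95% CI |
|---|---|---|---|
| 0/3300 | 0/550 | 0.00% | -0.69% to +0.12% |
| 3/3300 | 0/550 | +0.09% | -0.61% to +0.27% |
| 10/3300 | 0/550 | +0.30% | -0.40% to +0.56% |

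The difference has a finite estimate and upper bound in each row. The relative risk has neither.

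**The case against.** Four points can be made for the plan as it stands.

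1. **AESIs are not analysed by the relative risk alone.** Exact within-group intervals, a tabulation and a listing are also planned, and all survive zero counts. This stands. A reader can subtract the two proportions, but two separate intervals do not make an interval for the difference.

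2. **An exact unconditional interval can handle a zero cell.** With AV7909 events and none on BioThrax it can still give a finite lower limit. A rough inversion of the score test puts it near 0.1 for 3/3300 against 0/550 and near 0.5 for 10/3300 against 0/550; the value depends on the test statistic, which the SAP does not name. This stands, and it is a reason to keep the relative risk. It does not supply an upper limit, and the SAP does not say that a lower limit alone would be reported.

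3. **The cited rate may not carry over.** It comes from another CpG adjuvant and another vaccine, and it counts adjudicated new-onset events. Appendix B is broad (it includes psoriasis, rosacea and cranial nerve disorders), and the AESI table is not limited to new onset. This stands. At an assumed 0.2%, one event is already slightly more likely than none.

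4. **Nothing is decided on this comparison.** There is no test and no success criterion, and the endpoint is the incidence, which the plan delivers. This stands and limits the weight of the point.

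A reader might go further and infer that the trial will probably yield no usable between-group information on AESIs. The documents do not support that. The likelihood of a zero denominator depends on a rate they do not give, a lower limit may be available, and the fully uninformative 0/0 result has a probability of only 2% to 6% if both groups run at the cited rates. Nor do they support extending the point to SAEs, since no SAE rate is given from which to judge the chance of a zero denominator.

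**Conclusion.** The gap is real but narrow. The relative risk is the only between-group measure planned for AESIs. With no confirmed event among about 550 BioThrax participants it has no finite point estimate or upper limit, and at most a lower limit when AV7909 has events. No rule covers that case.

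The probability of the case is 58% to 67% at the rates the protocol cites, and falls to 33%, 19% and 6% at assumed rates of 0.2%, 0.3% and 0.5%. These figures assume independent events, a common rate within the group and 550 evaluable participants.

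No error rate, power claim or success criterion is affected. This is a free improvement to a descriptive safety analysis.

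**What to change.** In SAP 7.2.4:

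1. Add the risk difference for AESIs, pooled AV7909 minus BioThrax, with a two-sided 95% CI. Use Newcombe's method, already specified in SAP 6.2.2.2 for the non-inferiority comparison, or an exact unconditional method, and name the choice in advance.
2. Keep the planned relative risk, so that the SAP stays in line with Protocol 10.6.2 and the synopsis. State that when BioThrax has no AESI its point estimate and upper limit are shown as not estimable, with the exact lower limit given if AV7909 has events. When neither group has an event, the whole ratio is not estimable.

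The relative risk should not be withheld unless both groups have events, because that would discard a valid lower limit in the case at issue. The cost is a few sentences in the SAP and one table column, with no new data.
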